#### **6.3.1.3 Definition of Maximum Tolerated Dose (MTD):**

The Maximum Tolerated Dose (MTD) is defined as the highest dose level with no more than 1 DLT reported in 6 DLT-evaluable patients.

#### **6.3.1.4 Definition of Recommended Phase 2 Dose (RP2D):**

The Recommended Phase 2 Dose (RP2D) of CB-Nivo will be selected based on the clinical data and will not exceed the MTD. If  $< 2/6$  patients experience a DLT at 800 mg BID during dose escalation, then 800 mg BID will be considered to be the RP2D. If  $\geq 2/6$  patients experience DLTs at 800 mg BID, and  $\leq 1/6$  patients experience a DLT at 600 mg BID, then 600 mg BID will be considered the RP2D. The Sponsor, in consultation with the Study Investigators, will continue to evaluate the safety data accumulated during the evaluation of dose expansion cohorts and may amend the RP2D with further experience.

### **6.3.2 Phase 2 - Cohort Expansion**

To further characterize safety, tolerability, and efficacy, additional patients will be enrolled at the RP2D in specific cohorts outlined below.

The Sponsor, in consultation with Study Investigators, will evaluate the overall safety profile of the CB-Nivo combination during cohort expansions and as a monotherapy in advanced/metastatic melanoma. Safety data (drug-related AEs including Grade  $\geq 3$  irAEs and all SAEs) will be analyzed and reviewed by the Sponsor and Study Investigators. With ongoing safety analysis and review by the Sponsor and Study Investigators, decisions may be made to amend the RP2D with further experience in specific diseases. Cohorts are designed based on Simon's two-stage statistical approach, as described in the Statistical Analysis [Section 16.0](#).

#### **6.3.2.1 Cohort 1: ccRCC patients naïve to prior checkpoint inhibitor therapy**

This cohort will enroll ccRCC patients that have received a prior anti-VEGF/R therapy but have never received therapy with anti-PD-1/PD-L1, CTLA-4, or any other agent that specifically targets a T-cell checkpoint or co-stimulation pathway. This patient population was recently studied in a randomized Phase 3 study in which nivolumab was compared to everolimus. Nivolumab had an ORR of 25%, PFS of 4.6 mo, and OS of 25.0 mo ([Motzer 2015](#)). The primary endpoints of Cohort 1 will be safety/tolerability, ORR, and DOR per Investigator. Predose biopsies will also be collected in order to correlate efficacy with potential predictive biomarkers ([Section 14.2](#)).

A Simon's two-stage design will test the null hypothesis that the ORR  $\leq 0.25$  versus the alternative that ORR  $\geq 0.40$ ; the sample size of 52 patients will maintain an alpha level of 0.10 and a power of 0.80. At least 25 evaluable patients will be enrolled in Stage 1. If at least 8 patients respond (PR or better) out of 25 response-evaluable patients in Stage 1, then an additional 27 evaluable patients will be enrolled in Stage 2 (total of 52 response-evaluable patients). If Stages 1 and 2 are completed, a minimum of 17 patients must demonstrate a response (PR or better) to reject the null hypothesis.

#### **6.3.2.2 Cohort 2: ccRCC patients with disease progression or prolonged SD ( $\geq 24$ weeks) while receiving nivolumab in their most recent line of therapy**

This cohort will enroll ccRCC patients that received nivolumab in their most recent line of therapy with minimal washout ( $\leq 8$  weeks), with the intent of adding CB-839 to the ongoing nivolumab regimen. Since this patient population has either documented radiological disease progression OR long-term SD ( $\geq 24$  weeks), the likelihood of a response on nivolumab monotherapy is extremely low and any activity can be confidently attributed to the addition of

CB-839. The primary endpoints of Cohort 2 will be safety/tolerability, ORR, and DOR per Investigator. Predose and postdose biopsies will be collected during Stage 1 in order to demonstrate a pharmacodynamic effect of CB-839 in the context of PD-1 inhibition by nivolumab and correlate efficacy with potential predictive biomarkers (Section 14.2).

Since the mechanisms of resistance to nivolumab may be different in the settings of primary refractory disease, relapsed, and long-term stable disease, patients in Cohort 2 will fall into one of the following subgroups:

- a) Patients with progressive disease after achieving no better than SD
- b) Patients with progressive disease after achieving an objective response
- c) Patients with SD as their best response for  $\geq 24$  weeks

A Simon's two-stage design will test the null hypothesis that the ORR  $\leq 0.05$  versus the alternative that ORR  $\geq 0.15$ ; the sample size of 56 patients will maintain an alpha level of 0.10 and a power of 0.80. If at least 2 patients respond (PR or better) out of 20 response-evaluable patients in Stage 1, then an additional 36 evaluable patients will be enrolled in Stage 2 (total of 56 response-evaluable patients). If Stages 1 and 2 are completed, a minimum of 5 patients must demonstrate a response (PR or better) to reject the null hypothesis. The lower target ORR (15%) is based on the heterogeneity of histological subtypes (with potentially differential sensitivity to CB-839) in this cohort.

Of note, up to 5 additional patients may be enrolled in Stage 1 in order to ensure sufficient enrollment of each of the subgroups. Based on emerging data, the Sponsor may choose to restrict further enrollment in this cohort to one or two of the three subgroups identified above.

### **6.3.2.3 Cohort 3: ccRCC patients with disease progression while receiving an anti-PD-1/PD-L1 therapy in any prior line of therapy**

This cohort will enroll ccRCC patients that had documented radiological disease progression while receiving an anti-PD-1/ PD-L1 therapy in any prior line of therapy. An active anti-PD-1/ PD-L1 agent is defined as an agent that has demonstrated evidence of activity, e.g., nivolumab and pembrolizumab, atezolizumab, durvalumab, or avelumab. Since this patient population had documented disease progression on the prior anti-PD-1/ PD-L1 therapy, the likelihood of a response on nivolumab monotherapy is very low and evidence of activity can be confidently

attributed to the addition of CB-839. The primary endpoint of Cohort 3 will be safety/tolerability, investigator assessed ORR, and DOR per Investigator. Predose biopsies will be collected in order to correlate efficacy with potential predictive biomarkers ([Section 14.2](#)).

A Simon's two-stage design will test the null hypothesis that  $ORR \leq 0.05$  versus the alternative that  $ORR \geq 0.2$ ; the sample size of 24 patients will maintain an alpha level of 0.10 and a power of 0.80. At least 9 evaluable patients will be enrolled in Stage 1. If at least 1 patient responds (PR or better) out of 9 response-evaluable patients in Stage 1, then an additional 15 evaluable patients will be enrolled in Stage 2 (total of 24 response-evaluable patients). If Stages 1 and 2 are completed, a minimum of 3 patients must demonstrate a response (PR or better) to reject the null hypothesis.

#### **6.3.2.4 Cohort 4: Melanoma patients with disease progression while receiving an anti-PD-1 therapy in their most recent line of therapy**

This cohort will enroll melanoma patients with radiological disease progression (per Investigator assessment) while receiving an anti-PD-1/PD-L1 agent as monotherapy or in a combination regimen to treat advanced/metastatic melanoma in the most recent line of therapy. There must be  $\leq 8$  weeks elapsed between last dose of anti-PD-1/PD-L1 and C1D1 of the CX-839-004 trial. The intent of this cohort is to convert progressing disease to responding disease by the addition of CB-839 to ongoing anti-PD-1/PD-L1 therapy. Because this patient population has documented disease progression on anti-PD-1/PD-L1 therapy at study start, the likelihood of a response to nivolumab monotherapy is extremely low and any activity can be confidently attributed to the addition of CB-839. Patients on anti-PD-1/PD-L1 agent other than nivolumab will switch to nivolumab for treatment on this study. The primary endpoints of Cohort 4 will be ORR and DOR as determined by an Independent Radiology Committee (IRC). Pre- and post-dose biopsies will be collected from all patients enrolled into the Expansion phase of Cohort 4 (so long as deemed safe and technically feasible to biopsy) in order to demonstrate a pharmacodynamic effect of CB-839 in the context of PD-1 inhibition and to correlate efficacy with potential predictive biomarkers ([Section 14.2](#)).

The original study design with 24 patients tested the null hypothesis that ORR of CB-839 + nivolumab was  $\leq 5\%$  versus the alternative of  $\geq 20\%$  with an alpha level of 0.1 and power of

80%. Per study design, 9 patients would be enrolled in Stage 1 and 1 responder would trigger enrollment of an additional 15 patients in Stage 2; while 3 responders out of 24 total patients would lead to formal rejection of the null hypothesis. To date there have been 3 responding patients (including one complete response and 2 deep partial responses of -73% and -47%), all confirmed responses on repeat scan  $\geq 4$  weeks after initial response, in 16 evaluable patients. Notably, per protocol eligibility, all of these patients were experiencing disease progression on PD-1/PD-L1 inhibitor therapy in the immediate prior line of therapy strongly suggesting that the response was the result of the addition of CB-839.

As a result of encouraging preliminary clinical activity, Cohort 4 enrollment will be expanded to approximately 75 response-evaluable melanoma patients (including patients already enrolled). For the purpose of statistical design we assume a background/historical ORR of  $< 10\%$  in this patient population. The total sample size is determined based on the ability to produce a confidence interval that would exclude the historic response rate and to provide sufficient information for a reliable understanding of the safety profile. Specifically, the lower limit of the 95% CI associated with observation of an objective response rate of 18.7% in 75 treated subjects (14/75 responders) excludes 10%. Interim clinical monitoring will be performed in this expansion to ensure adequate safety and tolerability as well as favorable risk/benefit by assessing preliminary efficacy measures such as objective response rate and duration of response.

#### **6.3.2.5 Cohort 5: NSCLC patients with disease progression or prolonged SD while receiving an anti-PD-1 therapy in their most recent line of therapy**

This cohort will enroll patients with NSCLC that does not harbor an activating mutation in the epidermal growth factor receptor (EGFR) or anaplastic lymphoma kinase (ALK) oncogene and have received anti-PD-1/PD-L1 therapy as the most recent line of therapy with  $\leq 8$  weeks elapsed between last dose of anti-PD-1/PD-L1 and C1D1 of the CX-839-004 trial. Eligible patients will have experienced radiological disease progression or SD without response lasting  $\geq 24$  weeks with the intent of adding CB-839 to an ongoing anti-PD-1 regimen. Driver- mutation (EGFR or ALK) positive patients have been excluded because they tend to have lower mutational load and are less responsive to immunotherapies (Borghaei 2015). Patients receiving an anti-PD-1 therapy other than nivolumab would switch over to nivolumab. Because this

patient population has documented radiological disease progression or long-term SD ( $\geq 24$  weeks), the likelihood of a response on nivolumab monotherapy is extremely low and any activity can be confidently attributed to the addition of CB-839. The primary endpoint of Cohort 5 will be safety/tolerability, ORR, and DOR per Investigator. Pre-dose and post-dose biopsies will also be collected in order to demonstrate a pharmacodynamic effect of CB-839 in the context of PD-1 inhibition by nivolumab and correlate efficacy with potential predictive biomarkers ([Section 14.2](#)).

A Simon's two-stage design will test the null hypothesis that the ORR  $\leq 0.05$  versus the alternative that ORR  $\geq 0.15$ ; the sample size of 56 patients will maintain an alpha level of 0.10 and a power of 0.80. If at least 2 patients respond (PR or better) out of 20 response-evaluable patients in Stage 1, then an additional 36 evaluable patients will be enrolled in Stage 2 (total of 56 response-evaluable patients). If Stages 1 and 2 are completed, a minimum of 5 patients must demonstrate a response (PR or better) to reject the null hypothesis. The lower target ORR (15%) is based on the heterogeneity of histological subtypes (with potentially differential sensitivity to CB-839) in this cohort.

Enrollment will be monitored in order to ensure at least 8 patients are enrolled from each of the two major histological subtypes of NSCLC, squamous and non-squamous. Based on emerging data, the Sponsor may choose to restrict further enrollment in this cohort to a specific histological subtype.

#### **6.3.2.6 Cohort 6: CB-839 monotherapy in advanced/metastatic melanoma patients**

This cohort will enroll patients with advanced/metastatic melanoma with no curative options and will assess the anti-tumor activity of single agent CB-839. Because the combination of CB-839 and nivolumab has demonstrated activity in nivolumab-refractory disease, unbiased assessment of CB-839 as monotherapy is presumed to require full washout of previous PD-1/PD-L1 therapy. For the purpose of this study, full washout is defined as a minimum of 4 mo (approximately 5 half-lives) from the most recent dose of anti-PD-1/PD-L1 therapy to C1D1 of CB-839 monotherapy. This washout period will allow any clinical activity to be attributed to CB-839 alone. The primary endpoint of Cohort 6 is ORR per RECIST v1.1 as assessed by the Investigator. Pre-dose biopsies will be collected on all patients to evaluate for predictive

markers of treatment response. Because the combination of CB-839 with nivolumab has demonstrated activity in nivolumab refractory patients, patients will be eligible to receive the combination of CB-839 with nivolumab after disease progression on CB-839 monotherapy. These patients will be followed for the exploratory objectives of ORR, DOR, PFS per RECIST v1.1 subsequent to starting the combination of nivolumab and CB-839.

For the primary objective, a Simon's two-stage design will test the null hypothesis that  $ORR \leq 0.05$  versus the alternative that  $ORR \geq 0.2$ ; the sample size of 24 patients will maintain an alpha level of 0.10 and a power of 0.80. At least 9 evaluable patients will be enrolled in Stage 1. If at least 1 patient responds (PR or better) out of 9 response-evaluable patients in Stage 1, then an additional 15 evaluable patients will be enrolled in Stage 2 (total of 24 response-evaluable patients). If Stages 1 and 2 are completed, a minimum of 3 patients must demonstrate a response (PR or better) to reject the null hypothesis.

#### 6.4 Inclusion Criteria

1. Patients must have a histological or cytological diagnosis of metastatic cancer or locally advanced cancer that is not amenable to local therapy. Additional criteria specific to different Cohorts of the study are provided below.
2. Ability to provide written informed consent in accordance with federal, local, and institutional guidelines
3. Age  $\geq$  18 years
4. Eastern Cooperative Oncology Group (ECOG) Performance Status of 0-1
5. Life Expectancy of at least 3 mo
6. Patient must have adequate organ function as indicated by the following laboratory values:

Test	Value
Absolute neutrophil count (ANC)	$\geq 1,500$ /mcL
Total white blood cell (WBC) count	$\geq 2,000$ /mm 
Platelets	$\geq 100,000$ / mcL
Hemoglobin	$\geq 9$ g/dL
Serum creatinine	$\leq 1.5$ X upper limit of normal (ULN)
Serum total bilirubin	$\leq 1.5$ X ULN OR
Direct bilirubin (for patients with Gilbert Syndrome and total bilirubin levels $>1.5$ ULN)	$\leq$ ULN
AST (SGOT) and ALT (SGPT)	$\leq 2.5$ X ULN

International Normalized Ratio (INR) or Prothrombin Time (PT)	$\leq 1.5 \times \text{ULN}^*$
Activated Partial Thromboplastin Time (aPTT)	$\leq 1.5 \times \text{ULN}$

\* Does not apply to patients receiving therapeutic warfarin

7. Measurable Disease: At least one tumor lesion/lymph node that meets the RECIST v1.1 criteria for measurable disease
8. Female patients of childbearing potential must have a negative serum or urine pregnancy test within 3 days prior to the first dose of study drug and agree to use dual methods of contraception if sexually active during the study and for a minimum of 3 mo following the last dose of study drug. Post-menopausal females (> 45 years old and without menses for > 1 year) and surgically sterilized females are exempt from these requirements. Male patients must use an effective barrier method of contraception during the study and for a minimum of 3 mo following the last dose of study drug if sexually active with a female of childbearing potential.
9. Resolution of all treatment-related toxicities from any previous cancer therapy (including radiation and surgery) to  $\leq$  Grade 1 or to values within those required for eligibility on this study prior to the first dose of study treatment.
  - a. Exceptions include alopecia, anemia, or endocrinopathies managed by hormone replacement
10. Patients must be willing and able to comply with scheduled visits, treatment schedule, laboratory testing and other requirements of the study.

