### 7.2.1 Previous Human Experience

Three separate Phase 1 studies were initiated in February 2014 to evaluate the safety, pharmacokinetics, and pharmacodynamics of orally administered CB-839 either as a single agent or in combination with approved agents in patients with solid tumors (CX-839-001), multiple myeloma and NHL (CX-839-002), or acute leukemia (CX-839-003). CX-839-001 enrolled RCC patients for treatment with CB-839 + cabozantinib and CB-839 + everolimus, as well as TNBC patients for treatment with CB-839 + paclitaxel. In addition, the combination of CB-839 with nivolumab is being evaluated in this Phase 1/2 study, CX-839-004. During dose escalation in all three Phase 1 studies, single agent CB-839 was administered initially three times daily (TID) without meals and was later changed to twice daily (BID) with breakfast and dinner.

As of data cuts on 23 July 2017, a total of 105 patients received 600, 800, or 1000 mg BID CB-839 as a single agent; an additional 59 patients received single agent CB-839 dosed on the TID schedule ranging from 100 to 1000 mg TID. More than 150 patients have received CB-839 at doses ranging from 400 to 800 mg BID in combination with cabozantinib, erlotinib, everolimus, paclitaxel, nivolumab, dexamethasone, pomalidomide, or azacitidine.

In pharmacokinetic studies, the half-life of CB-839 was approximately 4 hours. A dose-related increase in exposure was observed over doses ranging from 100 to 600 mg; exposures for 600 mg and 800 mg doses were similar albeit with significant interpatient variability. In pharmacodynamic studies, robust inhibition of glutaminase was demonstrated in platelets at exposures maintained in most BID-dosed patients at 600 mg and 800 mg inter-dose troughs, with the 800 mg dose in particular showing  $\geq 90\%$  target inhibition. Patient tumor biopsies also demonstrated robust glutaminase inhibition ( $> 75\%$  for most patients).

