## 8.1 Prior anti-PD-1/PD-L1

Patients targeted for Cohorts 2, 4, and 5 may continue to receive anti-PD-1/PD-L1 therapy up to 3 weeks before C1D1. If anti-PD-1/PD-L1 has been discontinued, patients targeted for Cohorts 2, 4 and 5 must have no more than 8 weeks elapse between last administration of anti-PD-1/PD-L1 agent and C1D1 of this protocol. Patients receiving an anti-PD-1/PD-L1 therapy other than nivolumab will switch to nivolumab for study treatment. In order to assess CB-839 monotherapy activity, Cohort 6 patients must have at least 4 mo (approximately 5 half-lives) elapsed between most recent dose of anti-PD-1/PD-L1 therapy and C1D1 of CB-839 monotherapy on this study.

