## 9.0 CONCOMITANT TREATMENT

Concomitant treatment is permitted if the medication is not expected to interfere with the evaluation of safety or efficacy of the study drugs. During the study, if the use of any concomitant treatment becomes necessary (e.g., for treatment of an adverse event), the treatment must be recorded on the appropriate eCRF, including the reason for treatment, name of the drug, dosage, route, and start and stop dates of administration.

Except for erythropoietin or darbepoetin alpha (Aranesp®), use of growth factors (i.e., G-CSF, GM-CSF, etc.) is not permitted in the first treatment cycle unless the patient experiences a hematologic DLT.

Use of investigational therapeutic agents other than the study drugs, CB-839 and nivolumab, is NOT permitted while the patient is on study.

CB-839 is metabolized by human hepatocytes primarily through amide hydrolysis. CB-839 does not appear to induce CYP drug-metabolizing enzymes and only weakly inhibits CYP2C9 (~40-50% inhibition at 5µM) *in vitro*. Although CB-839 is not expected to inhibit CYP2C9 at the exposure levels planned, caution is warranted when administering CB-839 to patients taking drugs that are highly dependent on CYP2C9 for metabolism and have a narrow therapeutic index. A list of medications that are CYP2C9 substrates is provided in [Attachment 6](#).

Preliminary PK data generated in single agent Phase 1 studies suggest that concomitant use of proton pump inhibitors (PPIs) may reduce absorption of CB-839, resulting in decreased systemic

exposure. Although patients are *not required* to discontinue their use of these agents, the strong preference is for patients to discontinue PPIs prior to joining the study. Antagonists of the H2 histamine receptor (e.g., ranitidine, famotidine, etc.) may be substituted for PPIs. For patients unable to discontinue PPI therapy or that requires restarting PPI therapy while on study, administration of CB-839 with an acidic beverage (e.g., orange juice) or supplement (e.g., citric acid) may be an option. If an acidic beverage/supplement is approved by the Medical Monitor to be administered along with the CB-839 dose, it should be recorded on the appropriate eCRF, including the identity of the beverage/supplement, dosage, route, and start and stop dates of administration. Finally, if PPI is started while a patient is on-study, a PK profile may be required in order to confirm CB-839 exposure, see [Section 15.1](#) for specific time points.

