## 11.0 TEST ARTICLE/STUDY DRUG

### 11.1 Test Article Administration

#### CB-839

Test article (CB-839) will be administered orally using a capsule (200 mg per capsule) or tablet (200 mg per tablet) formulation. CB-839 will be administered only to patients who have signed and dated an Informed Consent Form. CB-839 will be administered on Days 1 through 28 of each 28-day cycle and should be taken orally using the number of capsules or tablets directed in the Pharmacy Manual. CB-839 dosing will not be adjusted for body weight or surface area.

The first CB-839 dose of the day will be administered immediately after breakfast. The evening/second dose should be taken with a meal approximately 12 hr ( $\pm$  2 hr) after the morning dose.

On PK days (Cycle 1 Days 1 and 15, Cycle 2 Day 1 and Cycle 3 Day 1) patients should be instructed NOT to take their morning dose of CB-839 at home. On PK days, patients will have all predose procedures performed, take their dose of CB-839 with food then receive nivolumab. The time of dosing will be recorded in the clinic. The evening dose will be self-administered by the patient after all postdose activities have been completed. On non-PK collection days, patients will administer CB-839 per their usual administration schedule.

Patients who vomit their CB-839 dose should be instructed NOT to make up that dose and to report the frequency of vomiting occurrences associated with study drug administration to the site. Patients who report  $\geq$  3 incidences of vomiting associated with study drug administration will have a blood sample drawn for an unscheduled PK analysis.

Nivolumab: Nivolumab will be administered at a flat dose of 240 mg IV infusion over 60 min on Days 1 and 15 of each 28-day cycle. Nivolumab (Opdivo®) is supplied by Calithera as a

10 mg/mL solution for infusion following dilution. Please refer to the [nivolumab package insert](#) for specific instructions on nivolumab administration.

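### Inclusion criterion 8's single 3-month contraception minimum can end up to a month before the protocol's own 4-month anti-PD-1/PD-L1 washout figure has passed since the last nivolumab dose

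*Protocol*

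**What the plan says.** Protocol Section 6.4, inclusion criterion 8, asks women of childbearing potential to agree to dual contraception "if sexually active during the study and for a minimum of 3 mo following the last dose of study drug". Men must use an effective barrier method while on study and then "for a minimum of 3 mo following the last dose of study drug if sexually active with a female of childbearing potential". Neither clause separates the two drugs.

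Nivolumab is a study drug. Section 9.0 states: "Use of investigational therapeutic agents other than the study drugs, CB-839 and nivolumab, is NOT permitted while the patient is on study".

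The two drugs are described very differently as to persistence:

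- CB-839, Section 7.2.1: "In pharmacokinetic studies, the half-life of CB-839 was approximately 4 hours".
- Anti-PD-1/PD-L1 agents, Section 6.3.2.6 (Cohort 6): "full washout is defined as a minimum of 4 mo (approximately 5 half-lives) from the most recent dose of anti-PD-1/PD-L1 therapy". Section 8.1 repeats it: "at least 4 mo (approximately 5 half-lives) elapsed between most recent dose of anti-PD-1/PD-L1 therapy and C1D1 of CB-839 monotherapy". The Cohort 6 inclusion criteria in Section 6.4 give the same figure, and exclusion criterion 5 in Section 6.5 requires more than 4 months for that cohort.

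On dosing, Section 11.1 says "CB-839 will be administered on Days 1 through 28 of each 28-day cycle" and puts nivolumab on Days 1 and 15. Section 10.8.2.2 lets either drug be held and restarted without the other. Table 10.8-1 allows re-challenge with CB-839 alone after nivolumab is permanently stopped for many immune-related events.

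**The concern.** One post-treatment period was written for a small molecule cleared within a day and for an antibody that the protocol treats as present for months. Three months fits the first. Against the protocol's own figure for the second, it can be short.

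What is at stake is fetal exposure. The protocol treats this as a risk to avoid: pregnant patients are excluded (Section 6.5), and test article stops at once if pregnancy is confirmed (Section 17.1). Pregnancy tests are scheduled only at screening and at End of Treatment, the latter within 28 days of stopping (Section 10.5, Attachment 1). After that visit, contraception is the only preventive measure stated. Reporting pregnancies for up to 6 months (Section 17.1) detects exposure but does not prevent it. No endpoint, error rate or sample size is affected.

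**Working it through.** **Inputs from the protocol.** Contraception minimum 3 months (Section 6.4, criterion 8). Class washout 4 months, about 5 half-lives (Sections 6.3.2.6 and 8.1). CB-839 half-life about 4 hours (Section 7.2.1). CB-839 on Days 1 to 28 and nivolumab on Days 1 and 15 of a 28-day cycle (Section 11.1).

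**Assumptions.** One month = 30.44 days, so 3 months = 91.3 days and 4 months = 121.75 days. Elimination is first-order. The contraception clock starts at the last dose of either drug.

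**The plan's own figure.** The 4-month washout cannot be reproduced, because no anti-PD-1 half-life is given separately. Taken at face value it implies a half-life of 4 / 5 = 0.8 month = 24.35 days.

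**CB-839.** Five half-lives are 5 × 4 = 20 hours. Three months is 91.3 × 24 / 4, about 548 half-lives.

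**Nivolumab.** Let *lag* be the days from the last nivolumab dose to the last CB-839 dose (0 if nivolumab is last).

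- Shortfall in days = max(0, 30.4 − lag)
- Fraction remaining when contraception ends = 0.5^((91.3 + lag) / 24.35)

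On schedule, the lag runs from 0 (both last taken on a nivolumab day) to 13 days (Day 15 to Day 28, or Day 1 to Day 14).

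| Situation | Lag (days) | Shortfall (days) | Remaining at end of contraception |
|---|---|---|---|
| Nivolumab last, or both last taken the same day | 0 | 30.4 | 7.4% |
| Both run to Day 28 | 13 | 17.4 | 5.1% |
| CB-839 alone for about a month | 30.4 | 0 | 3.1% |

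The last row equals 0.5^5, the level at the protocol's 4-month washout.

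**If nivolumab's half-life differs from the class figure** (lag 0; the range is an assumption):

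| Half-life | Half-lives in 3 months | Remaining at 3 months |
|---|---|---|
| 0.6 month (18.3 days) | 5.00 | 3.1% |
| 0.7 month (21.3 days) | 4.29 | 5.1% |
| 0.8 month (24.4 days) | 3.75 | 7.4% |
| 0.889 month (27.1 days) | 3.37 | 9.6% |

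Break-even is 3 / 5 = 0.6 month. At a half-life of about 18 days or less, 3 months already covers 5 half-lives.

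**The case against.** The strongest reply is that the benchmark was borrowed. The 4-month washout was defined for Cohort 6 so that response could be credited to one drug: "This washout period will allow any clinical activity to be attributed to CB-839 alone". Nothing in the protocol says contraception must last 5 half-lives. The figure is a rounded minimum for a whole class of prior agents, and it belongs to a cohort that SAP Section 7.7 says was never enrolled. All of this stands, and it limits the point to a mismatch between two provisions. It does not remove the point. The rationale for the washout is pharmacological, antibody clearance does not depend on whether Cohort 6 enrolled, and no better persistence figure is given. The 21-day, 3-week and 8-week windows elsewhere are entry intervals and are not expressed in half-lives.

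A second reply is that 3 months is only a floor and that the label governs. Sections 16.8 and 17.0 do refer to the nivolumab label for precautions and safety. They are general pointers: neither states a contraception period nor says that the label overrides criterion 8. A site applying criterion 8 as written may stop at 3 months.

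A reader might infer that criterion 8 is unsafe, or that it breaches the nivolumab label. The documents do not support either. They give no harmful residual level, so nothing marks 7.4% as dangerous or 3.1% as acceptable. The label and the consent form were not available for this review.

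A reader might also infer that men need a longer period, or that contraception should match the 6-month pregnancy-reporting window. The documents give no basis for male-mediated nivolumab exposure, and the reporting window is surveillance that need not match.

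**Conclusion.** The point holds as a precautionary internal mismatch for women of childbearing potential who receive nivolumab. Measured against 4 months from the last nivolumab dose, the 3-month minimum falls short by about 17 to 30 days when both drugs are given to schedule and by a full month when nivolumab is dosed last. It does not fall short when CB-839 continues alone for a month or more. A month is therefore the maximum and should not be quoted as the typical gap.

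This rests on applying the class-wide washout to nivolumab and on reading *study drug* as whichever drug is dosed last. The second assumption is not beyond doubt, since Sections 10.9 and 11.5 use the term for CB-839 alone. Under that reading, a woman who stopped CB-839 but stayed on nivolumab would start the clock early and could face a gap of more than a month. Confidence is medium, because nivolumab's actual half-life could close the gap. The change is still worth making, since it is cheap and protects against an avoidable exposure.

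**What to change.** For women of childbearing potential, reword inclusion criterion 8 and the matching consent text to name both drugs. Require contraception until the later of (a) 3 months after the last CB-839 dose and (b) at least 4 months after the last nivolumab dose, or longer if the current nivolumab label requires it. Check the label before fixing the second interval.

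Leave the male clause at 3 months, naming the drugs, unless the label says otherwise. Leave the 6-month pregnancy-reporting window as it is.

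The cost is a change of wording; no visit, procedure or patient is added. The burden is up to about one further month of contraception, and none for women who continue CB-839 alone for a month or more, unless the label sets a longer period.
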